### **Design Summary**

The main objectives of this study are to assess the effects of bupropion and nortriptyline on smokers' emotional reactivity during a quit attempt, as assessed by startle responding to positive and negative emotional cues, and smoking related stimuli; whether this emotional reactivity predicts time to relapse; and, if genetic differences influence the magnitude of these effects. The present study will use a 3x4x4 repeated measures design, with Group (Bupropion/Nortriptyline/ Placebo) serving as the between groups factor, and Days (days post-quit/laboratory assessments) and stimulus valence (positive, negative, neutral, cigarette) serving as within subject factors. The sample will be stratified for race, gender, previous history of major depression, and the DRD2A1/A2 genotype, since the DRD2 marker is of primary interest. As shown Figure 6, 354 smokers will be exposed to four laboratory assessment sessions over a period of 38 days. Medication will be administered in a blinded fashion. Participants will complete a baseline laboratory session before any treatment begins (while still smoking). Immediately after their baseline laboratory session participants will be randomized into one of the three treatments and begin taking the appropriate medication. After ten days of medication, all groups will quit smoking for the duration of the study. Participants in all groups will also receive a series of in-person smoking cessation counseling sessions, two prior to quitting and five after the quit date, plus a series of telephone counseling calls at selected intervals in between the in-person counseling sessions. After completion of all laboratory and counseling sessions, all participants will return for follow up assessments at 3

months (10 days after medication ends) and 6 months post quit. In addition, telephone assessments of abstinence status will be carried out 2 and 4 months post-quit. A study time line is provided on page 20.

**Subject Recruitment.** Participants who want to quit smoking will be recruited from Houston

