## Power

Analysis of the startle responses will be conducted using mixed model regression. The study design involves both between subject and within subject fixed effects and correlations due to repeated measures on the participants. Within subject fixed effects include Days (baseline, post quit days 2,5, 28) and slide valence (positive, negative, neutral, cigarette). Between subjects effects include Treatment (Placebo, Bupropion, Nortriptyline) and Genotype (e.g., A1/A1 or A1/A2 and A2/A2 for our main hypothesis, and others as described for secondary hypotheses). Because of the nonstandard design, power calculations were conducted using simulations in SAS (PROC MIXED). To simplify calculations, we

**Table 4 Effect Sizes & Corresponding Differences in Startle Magnitude (µVolts) For Comparisons Genotype Main Effects Varying Prevalence Rates of the At Risk Allele**

Prevalence of "at risk" allele	Model 1	Model 2	Model 3
.5	.15 (3)	.29 (20)	.29 (16)
.4	.16 (3)	.30 (20)	.30 (16)
.3	.17 (4)	.32 (22)	.31 (17)
.2	.20 (4)	.36 (25)	.35 (19)

assume that the response to the slides at each level of valence within session will be averaged. The repeated measures on each subject are associated with correlations between observations from the same subject across sessions, and between observations from the same subject within session. We estimated these correlations using data from our previous work. For the primary hypothesis described below, we will fit three models. The first (Model 1) will restrict analyses to positive, negative and cigarette, stimuli and use the score to the neutral stimuli as a covariate, the second (Model 2) will use data from all valences together, and the third (Model 3) will use all data but examine post-quit scores controlling for baseline scores. The within subject-between-session and within subject-within session correlations varied for each model in our preliminary work. For Model 1, we estimated the within subject-between session and within subject-within session correlations to be .03 and .45, respectively; for the Model 2 we estimated them to be .7 and .9, respectively, and for Model3, we estimated them to be .6 and .9, respectively.

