### Primary Hypotheses

1. The emotional reactivity of smokers during nicotine withdrawal will be significantly higher among those that receive placebo vs. either bupropion or nortriptyline therapy for smoking cessation. Emotional reactivity will be assessed using the eye blink response to an acoustic startle probe and by evaluating responses to emotionally valent stimuli (positive, negative, cigarette) relative to neutral visual slides.

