  - 1.1. Mixed model repeated measure regression analyses will be used to evaluate this hypothesis, regressing peak startle magnitude, on Group (Bupropion, Nortriptyline, Placebo with Days (e.g., baseline, post-quit days 2, 5, 28) as the repeated measures factor. Three types of models will be evaluated. Model 1 will be restricted to startle responses to positive negative and cigarette stimuli and will include valence (positive/negative/cigarette) as a factor. This model will also include the corresponding value of the startle response to neutral stimuli as a covariate. In this way, we can compare the relative magnitude of startle responses to each valence adjusted for the response to neutral cues. The main effect of treatment Group is of primary interest in this model and will be evaluated first, followed by Days, and the Group X Day interaction. Other interactions including Group X Valence and Group X Valence X Days will also be explored. To assess Group differences (if any) at the beginning of the study, an a priori contrast on the baseline values only will also be carried out for this model, evaluating the main effect of Group and the Group by Valence interaction. In Model 2, startle will not be restricted to positive, negative or cigarette valences but will include all valences. The main effect of Group will be evaluated first, followed by Days, each of the two way interaction terms, and the Group X Day X Valence interaction. An a priori contrast will also be carried out as in Model 1 on the baseline values, to assess Group differences (if any) at the beginning of the study. The third model will involve only the post-quit assessments. This model is similar to Model 2, but will include the corresponding baseline value for each stimulus valence as a covariate. In this way, post cessation startle values may be expressed as a function of the corresponding pre cessation baseline values. As described in our preliminary studies, we believe this analysis can be quite informative, as it focuses on post cessation startle in relation to responses under nondeprived (baseline) conditions.
2. The emotional reactivity of smokers during cessation will be moderated by genotype. Our initial hypotheses focuses on the DRD2:
  - 2.1. We hypothesize that emotional reactivity will be lower for those carrying the DRD2 A1 and using bupropion vs. A1 smokers using either nortriptyline or placebo. A1 nortriptyline users are expected to

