have lower reactivity than A1 placebo users[PCP18]. Homozygous A2s are expected to respond similarly to both drugs with higher levels of emotional reactivity being observed for placebo vs. either bupropion or nortriptyline.

This hypothesis will be evaluated using models similar to those described for hypothesis 1, but with the addition of Genotype (A1/A2 or A1/A1 vs. A2/A2) as a term in each model. We will specifically evaluate the main effect of Genotype first, followed by the Genotype X Group interaction (the term of interest). Other interactions involving Genotype with Days and Valence will be explored as described for Models 2 and 3 above. Planned contrasts involving the difference in startle magnitude between each Group condition, within Genotype, will also be carried out.

3. Higher levels of emotional reactivity of smokers at baseline and or during cessation will be inversely related to abstinence at the 3 and 6 month follow-ups.

- 3.1. Two types of analysis will be carried out. Our primary focus will be on predicting days to relapse. For this analysis, startle responses will serve as the independent variable with days to relapse as the dependent measure. The primary analysis will focus on the average startle response from the baseline assessment. In secondary models, average response to each valence will be included as predictors to determine the relative predictive strength of the different valences. Startle response from each of the post-quit assessments will also be examined as time dependent variables to determine if startle responses from the other assessments predicts relapse. Each model will also be evaluated controlling for or not controlling for treatment Group. For this analysis we will use Cox proportional hazards regression. We are also interested in predicting abstinence (yes/no) at the 3 and 6 month follow-up. Therefore we will also use the GLIMMIX Macro from SAS, which is an adaptation of the PROC Mixed procedure for hypothesis 1 and 2 for dichotomous out come variables (abstinence) to test whether startle responses are related to abstinence, modeling baseline, valence and time dependent characteristics of the model in the manner proposed above. Interactions between genotype (DRD2 A1 vs. A2) and startle in the prediction of abstinence, will also be explored using in the separate and combined valence models.

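### The Group main effect tested first in Models 1 and 2 averages in the pre-drug baseline session, so it estimates about three quarters of a constant post-quit drug effect, and no post-quit contrast is named primary.

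*Combined protocol and SAP*

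**What the plan says.** All references are to section D of the combined protocol and SAP.

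- **Hypothesis 1 (Primary Hypotheses, 1)** is worded as follows: "The emotional reactivity of smokers during nicotine withdrawal will be significantly higher among those that receive placebo vs. either bupropion or nortriptyline therapy". The target is a difference after quitting.
- **Timing of baseline (Design Summary):** "Participants will complete a baseline laboratory session before any treatment begins (while still smoking". Randomisation and the first dose follow that session.
- **Models 1 and 2 (Primary Hypotheses, 1.1):** startle is regressed on Group "with Days (e.g., baseline, post-quit days 2, 5, 28) as the repeated measures factor". In Model 1, "The main effect of treatment Group is of primary interest in this model and will be evaluated first". In Model 2, "The main effect of Group will be evaluated first, followed by Days, each of the two way interaction terms". Both also include Group X Day and a separate contrast on the baseline values alone.
- **Model 3:** "The third model will involve only the post-quit assessments", with the matching baseline value as covariate.
- **Hypothesis 2 (2.1):** similar models with Genotype added. "We will specifically evaluate the main effect of Genotype first, followed by the Genotype X Group interaction (the term of interest".
- **Power:** 80% power with 354 subjects for .17, .32 and .30 SD (4, 22 and 16 µV) in Models 1, 2 and 3. On method: "Because of the nonstandard design, power calculations were conducted using simulations in SAS (PROC MIXED". The session pattern of the simulated effect is not given.

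The plan says that three models will be fitted and does not say which one decides either hypothesis.

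**The concern.** Neither drug can have acted at baseline. A Group effect averaged over baseline and days 2, 5 and 28 therefore mixes one session of certain null effect with the three sessions that Hypothesis 1 is about. It is a smaller quantity than the post-quit effect, and chance baseline imbalance enters it with weight 1/4.

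Two things are at stake. First, the only Group term called primary in any model is one of the diluted ones. If it disagrees with Model 3, nothing in the plan says which result counts. Second, the printed detectable effects can be read on a post-quit or a four-session scale. On the first reading the power of the term tested first is overstated. On the second, the post-quit difference it can detect is a third larger than the printed figure.

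**Working it through.** **Inputs.** From the Power section: N = 354, type I error .05, within-session correlation w and between-session correlation b of .45 and .03 (Model 1), .9 and .7 (Model 2), .9 and .6 (Model 3). Valences V = 3 in Model 1 and 4 in Models 2 and 3. Assumed because not stated: equal allocation (118 per arm), two-sided test, no dropout. Outcome variance is set to 1, and the baseline covariate is taken as the session mean.

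**Formulas.** Variance of one session mean: v = [1 + (V−1)w]/V. Variance of a subject's mean over S sessions: f = [v + (S−1)b]/S. SE of a two-arm difference: √(2f/118). Detectable effect at 80% power: 2.80 × SE.

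**Step 1: the plan's own figures.**

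| Model | v | f, 4 sessions | detectable | f, 3 sessions | detectable | plan |
|---|---|---|---|---|---|---|
| 1 | .633 | .181 | .155 | .231 | .175 | .17 |
| 2 | .925 | .756 | .317 | .775 | .321 | .32 |
| 3 | .925 | – | – | .708 | .307 | .30 |

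Model 2 reproduces with either four or three sessions, so the figure does not show which was simulated. Model 3 reproduces closely (78% power at .30). Model 1 falls between the two readings and is not reproduced exactly. As the plan used simulations that are not shown, I do not call it wrong.

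**Step 2: the weight on the post-quit effect.** With effect 0 at baseline and d at days 2, 5 and 28, equally weighted session means give 0.75d. Generalised least squares without Group X Day, using the plan's correlation structure, also gives 0.75 in both models.

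**Step 3, reading (a): .17 and .32 SD are post-quit differences.** Power of the four-session main effect = Φ(0.75d/SE − 1.96).

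- Model 1: .1275/.0554 = 2.30, power 63%. If the stated 80% is taken as given instead: Φ(2.80 × 0.75 − 1.96) = 56%.
- Model 2: .24/.1132 = 2.12, power 56%.

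Alternatives at the same effects:

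| Test | Variance term | Model 1 | Model 2 |
|---|---|---|---|
| Post-quit mean, unadjusted | f for 3 sessions: .231; .775 | 78% | 80% |
| Post-quit mean, baseline as covariate | f − b²/v: .230; .245 | 78% | >99% |
| Post-quit mean minus baseline | f + v − 2b: .804; .300 | 31% | 99% |
| Group X Day, two arms, 3 df | noncentrality 59 × 0.75d²/(v − b): 2.12; 20.14 | 20% | 98% |

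A simulation of 4,000 runs agreed: four-session main effect 62% and 56%; baseline-adjusted post-quit mean 76% and over 99%.

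**Step 4, reading (b): .17 and .32 SD are four-session averages.** The 80% stands, and the post-quit difference needed is the printed figure divided by 0.75.

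- Model 1: .17/.75 = .227 SD; 4/.75 = 5.3 µV.
- Model 2: .32/.75 = .427 SD; 22/.75 = 29.3 µV.
- Hypothesis 2, Table 5, Model 2 at 40% prevalence: 41/.75 = 54.7 µV.

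**Step 5: at the plan's benchmark of 27 µV.** The SD implied in Model 2 is 22/.32 = 68.75 µV, so d = .393. Power is 74% for the four-session main effect, 93% for the unadjusted post-quit mean, and over 99% for the baseline-adjusted post-quit mean. In Model 1 (SD 4/.17 = 23.5 µV) a 27 µV effect is detected almost surely by any of these tests.

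**The case against.** The strongest reply is that the plan already contains the right analysis. Model 3 is post-quit and baseline-adjusted, is powered separately, and carries over to Hypothesis 2. The phrase about primary interest orders terms within Model 1 and need not set Model 1 above Model 3. Models 1 and 2 also plan Group X Day and a baseline contrast, so a reader would see a null difference at baseline. All of this is correct. It shows that the repair is cheap, but it leaves the deciding test undefined and the terms tested first in Models 1 and 2 diluted.

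The loss is also uneven. In Model 1 the main effect has close to 100% power at 10 µV and above, so its cost is confined to effects near 4 to 5 µV. Group X Day in Model 1, weak at 4 µV, reaches about 88% at 10 µV. In Model 2 at 27 µV, Group X Day exceeds 99%. This stands: the main practical loss is in the Model 2 main effect. There, reading (b) needs 29 µV, above the 27 µV that the plan cites as evidence of adequate power. The plan does not say whether those 27 µV are post-quit only. If they include baseline, the comparison with the printed 22 µV is like for like.

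The 3/4 weight also depends on the fit. The plan selects the covariance by fit statistics. A model without Group X Day under AR(1) correlation of .7 (my assumption) would give a weight of .62. With Group X Day in the model and equally weighted sessions, 3/4 is exact.

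Finally, dilution does not inflate type I error. It shrinks the estimate and lowers power.

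**Conclusion.** The concern holds and should be fixed. The Group term tested first in Models 1 and 2 is not the quantity in Hypothesis 1. It is about 0.75 of a constant post-quit effect, and the Genotype X Group term in those models inherits the same factor. Either its power at the printed effect sizes is about 63% (Model 1; 56% if the plan's 80% is accepted) and 56% (Model 2), or the printed detectable differences understate the post-quit ones by a quarter: 4 against 5.3 µV, and 22 against 29 µV. The documents do not settle which. The sizes rest on a constant effect across days 2, 5 and 28, none at baseline, 118 per arm, a two-sided 5% test, no dropout and the plan's correlations. That baseline is pre-drug, that it is included in both models, and that the three models are unranked follow from the text alone.

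**What to change.** Name one post-quit, baseline-adjusted Group contrast as the primary test of Hypothesis 1 and the corresponding Genotype X Group contrast as primary for Hypothesis 2. Model 3 as written would serve. So would Models 1 and 2 refitted with days 2, 5 and 28 as outcome and baseline startle as covariate, or with baseline means constrained equal across arms. Make the four-session Group main effect secondary. If it is kept, restate the Model 1 and 2 detectable effects on the post-quit scale, and state the session pattern used in the power simulation.

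A simple post-quit minus baseline contrast is not a good substitute in Model 1. At a between-session correlation of .03 it mainly adds noise, and its power at .17 SD would be about 31%.

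The cost is analysis-plan wording. No visits, data or participants are added.

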We estimated power based on 354 subjects and a Type I error rate of 0.05. Power calculations were repeated for each of the three models. For Hypothesis 1, we estimated power for the group contrast between placebo and either bupropion or nortriptyline. A sample size of 354 subjects provides 80% power to detect effect sizes of .17, .32 and .30 standard deviations between these groups for Models 1, 2 and 3, respectively. Given the variability estimates in the raw startle magnitude scores we found by applying the three models to our previous work, these effect sizes translate into group differences in startle magnitude of 4, 22 and 16

µvolts, for Models 1,2 and 3, respectively. These values are well within the range observed in our preliminary studies where the overall difference between treatment and controls averaged 27 µvolts. This range also provides adequate power for detecting interactions with valence for any of the Models, as the range of differences between positive and negative valence between groups, is above 16 µvolts. For Hypothesis 2, we estimated power for the genotype comparisons across a range of possible prevalence for the “at risk” allele, among smokers. The expected allele frequency among smokers is shown in **Table 3**. Data from controls are provided for comparison but except in the case of the NET, are not considered in the power calculations. Power analyses for genotype effects are summarized in **Table 4**. Effect sizes are shown in standard deviation units. The corresponding difference in raw scores (µvolts) is shown in parentheses. Our major hypothesis involving genotype center on the DRD2, for which the A1 is the “at risk allele. As shown in **Table 3**, the expected frequency in our sample of smokers is above 40%. Effect sizes at this frequency and above vary from .15-.30, which corresponds to differences of 3-16 µvolts (see **Table 4**), for the three respective models. In our preliminary studies, the average difference in startle magnitude across all valences between A1 and A2 smokers who quit during the study was 26 µvolts, so we will have adequate power for these comparisons.

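### Hypothesis 1 is tested by a non-directional three-arm Group effect but powered on a placebo-versus-drug contrast that its analysis never names, so a significant Group effect does not by itself establish the hypothesis

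*Combined protocol and SAP*

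**What the plan says.** The hypothesis (section D, Primary Hypotheses, item 1) is directional: emotional reactivity "will be significantly higher among those that receive placebo vs. either bupropion or nortriptyline therapy for smoking cessation".

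Item 1.1 enters Group with three levels in a mixed model. For Model 1, "The main effect of treatment Group is of primary interest in this model and will be evaluated first". For Model 2, "The main effect of Group will be evaluated first, followed by Days, each of the two way interaction terms". Model 3 is described as similar to Model 2, restricted to post-quit sessions with baseline as covariate.

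The only contrast named under Hypothesis 1 is a check on pre-treatment values: "an a priori contrast on the baseline values only will also be carried out for this model", repeated for Model 2. Between-arm contrasts appear only under Hypothesis 2: "Planned contrasts involving the difference in startle magnitude between each Group condition, within Genotype, will also be carried out".

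The Power section describes a different test: "For Hypothesis 1, we estimated power for the group contrast between placebo and either bupropion or nortriptyline". It gives 80% power at .17, .32 and .30 SD for Models 1, 2 and 3. The error rate is set here: "We estimated power based on 354 subjects and a Type I error rate of 0.05". No multiplicity adjustment is mentioned.

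The section on abstinence compliance and startle assessments says that a strategy for comparing the drug groups with placebo is outlined in the data analysis section. Item 1.1 contains no such contrast.

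**The concern.** A Group effect across three arms is significant whenever the arm means differ enough in any pattern: placebo above the drugs, placebo below them, or one drug above the other with placebo in between. Only the first pattern is Hypothesis 1. The stated 80% power belongs to a 1-df comparison with placebo, which is not the test item 1.1 puts first.

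A difference between the drugs is not a remote possibility here. The Power section says the investigators expect smokers to respond differently to the two treatments in emotional reactivity. Hypothesis 2 predicts that A1 carriers, expected to be above 40% of the sample, do better on bupropion than on nortriptyline. The plan also leaves open whether *either* requires one drug or both to beat placebo, and whether the powered contrast uses one drug or both pooled.

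**Working it through.** **Inputs.** N = 354 and Type I error 0.05 (Power). Between-session and within-session correlations (Power): Model 1 .03 and .45; Model 2 .7 and .9; Model 3 .6 and .9. Sessions × valences: 4×3, 4×4, 3×4. Assumed, because not stated: 1:1:1 allocation (118 per arm), two-sided tests, no dropout. The effect d is the difference in a participant's mean over the sessions in the model.

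**Step 1. SD of a participant's mean.** With s sessions and v valences, variance = [1 + (v−1)·r_within + (s−1)·v·r_between]/(s·v).
- Model 1: (1 + .90 + .27)/12 = .1808, SD .425
- Model 2: (1 + 2.7 + 8.4)/16 = .756, SD .870
- Model 3: (1 + 2.7 + 4.8)/12 = .708, SD .842

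**Step 2. Reproduce the stated figures.** Detectable d at 80% power = 2.80 × SD × √(1/n₁ + 1/n₂).

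| | Model 1 | Model 2 | Model 3 |
|---|---|---|---|
| Stated | .17 | .32 | .30 |
| Placebo v one drug (118 v 118) | .155 | .317 | .307 |
| Placebo v pooled drugs (118 v 236) | .134 | .275 | .266 |

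One drug, unadjusted, fits Models 2 and 3 closely (power 80.7% and 78.2% at the stated effects). It does not fit Model 1 (86.7%). Pooling fits none directly. The ratios between tables point the other way. Hypothesis 1 effects over Table 4 at prevalence .5 are 1.13/1.10/1.03, where pooling predicts 1.06 and one drug 1.22. Table 5 over Table 4 is 2.13/1.97/1.97, where pooling predicts 2.12 and one drug 2.45. The documents do not settle which was powered. Neither is the Group test.

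**Step 3. Power of the Group test at the stated effects.** Noncentral F with 2 and 351 df; noncentrality = 118 × Σ(mean − grand mean)²/variance.
- Both drugs lower by d: sum = ⅔d², noncentrality 12.6/10.7/10.0, power about 90/84/81%.
- One drug lower by d, the other by d/2: sum = ½d², noncentrality 9.4/8.0/7.5, power about 79/71/68%.
- Drugs d apart, placebo midway: the same sum, so again about 79/71/68%.
- Placebo below both drugs by d: about 90/84/81%, the same as if the hypothesis were true.

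**Step 4. What a significant Group test shows (simulation).** With placebo midway, the Group test rejects and no unadjusted 5% contrast has placebo significantly above a drug in about 46/43/42% of all trials. In about 19% of all trials neither contrast is significant in either direction. In the remainder (for Model 2, 43 − 19 = 24 points) a contrast is significant with placebo *lower*.

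**Step 5. Named contrasts.** Under the global null, two unadjusted contrasts have a family error of about 9%. If they are tested only after a significant Group test it is about 4%, and about 5% when just one drug equals placebo.

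With d/SE = 3.07/2.83/2.74 and a Dunnett critical value near 2.21, power per drug = Φ(.86)/Φ(.62)/Φ(.53), about 80/73/70%. The 80% detectable effect is (2.21 + .84) × SE, about .17/.35/.33 SD. If both drugs work equally, power for at least one is about 91–92/86/84%. With the Group gate, power per drug is about 84/76/73% if both work equally.

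**The case against.** The plan states no rule equating a significant Group effect with Hypothesis 1. The hypothesis carries its own direction, the Power section names a placebo-versus-drug contrast, and another section states the intent to compare the drug groups with placebo. An analyst would look at the arm means, and a result with placebo significantly lower would count against the hypothesis. All of this stands, so a reader who infers that the trial will claim Hypothesis 1 from a drug-drug difference goes further than the text allows. What remains is that the contrasts, their error control and the meaning of *either* are unwritten for Hypothesis 1, although planned contrasts are written for Hypothesis 2.

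Two other strong readings fail. The 9% family error is not built into the plan: it arises only if the contrasts skip the Group test that the plan evaluates first. Nor is the study shown to be underpowered: the Group test exceeds 80% in all three models when both drugs lower startle equally, and falls below 80% when their effects differ as in Step 3. The placebo-midway case shows what the test can do. The plan does not predict it, since Hypothesis 2 places both drugs below placebo.

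**Conclusion.** The point holds as a mismatch between the test named for Hypothesis 1 and the contrast that was powered. That the Group effect would decide Hypothesis 1 is an inference from its being of primary interest and evaluated first.

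The size depends on the pattern of means: negligible loss of power if the drugs act alike, but a Group test that can be significant without support for the hypothesis in over 40% of trials if they diverge around placebo. The figures rest on the Step 1 assumptions and a closed-form variance, whereas the plan used simulations whose settings are not given. Model 1's stated .17 does not reproduce as an unadjusted one-drug contrast; it happens to match the Dunnett-adjusted one, but nothing in the documents says an adjustment was made.

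**What to change.** In Primary Hypotheses, item 1.1, add:
- Hypothesis 1 is tested by placebo minus bupropion and placebo minus nortriptyline, judged drug by drug in the hypothesised direction.
- *Either* means at least one drug.
- Family error is held at 5%, either by Dunnett or by testing the two contrasts only after a significant Group test. Both are valid; choose one in advance.

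In Power, say whether one drug or both pooled was powered, and restate power by model for the chosen rule, using the Step 5 figures. Under Dunnett the 80% detectable effects for Models 2 and 3 rise to about .35 and .33 SD. On the plan's own conversion that is .35 × 22/.32 = 24 µV and .33 × 16/.30 = 17.6 µV, against 22 and 16 µV now. Recheck Model 1's .17.

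The cost is wording and slightly less favourable per-drug power for Models 2 and 3. No extra data or participants are needed.
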